All statistical analyses will be conducted using IBM SPSS Statistics version 28.0 (IBM Corp., Armonk, NY, USA). Statistical significance will be set at a two-sided $p < 0.05$. Continuous variables will be presented as mean and standard deviation (SD) or median and interquartile range (IQR) where appropriate, while categorical variables will be summarized as frequencies and percentages.

Analyses will follow the intention-to-treat (ITT) principle, including all participants as randomized regardless of protocol adherence. A per-protocol analysis may also be conducted as a sensitivity analysis.

Study Design Considerations (Crossover Structure)

This study adopts a two-period, two-sequence crossover randomized controlled design:

Sequence A: VR CAVE → Simulated Home

Sequence B: Simulated Home → VR CAVE

Each participant serves as their own control, improving statistical efficiency and reducing between-subject variability.

Key effects to be evaluated include:

Intervention (VR CAVE vs simulated home)

Period effect (first vs second session)

Sequence effect (order of intervention)

Carryover effect (residual effect from first intervention)

Outcome Measures

Primary outcomes:

Clinical competence (CCQ total and subscale scores)

Self-confidence and satisfaction (SSS scores)

Cultural competence (CCA total and subscale scores)

All outcomes are treated as continuous variables.

Baseline Analysis

Baseline characteristics (e.g., gender, prior clinical experience) will be compared between the two randomized sequences:

Categorical variables: Chi-square test or Fisher's exact test

Continuous variables: Independent samples t-test or Mann-Whitney U test (if non-normal)

This step assesses the success of randomization.

Primary Analysis

A linear mixed-effects model (LMM) will be used to evaluate intervention effects while accounting for repeated measures and crossover design.

Model specification:

Random effect: Participant ID

Fixed effects:

Intervention (VR CAVE vs simulated home)

Period (1 vs 2)

Sequence (A vs B)

Time (pre vs post)

Interaction terms (e.g., intervention \times time)

The primary parameter of interest is the intervention effect, estimated as the difference in outcome scores between VR CAVE and simulated home conditions.

Carryover Effect Assessment

To assess potential carryover effects:

A sequence effect will first be examined within the mixed model.

Additionally, an interaction term (intervention \times period) may be explored.

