If a statistically significant carryover effect is detected ($p < 0.05$), analysis will be restricted to first-period data only, effectively treating the study as a parallel-group trial.

Within-Group and Between-Condition Comparisons

Pre–post changes within each condition will be analyzed using paired t-tests or equivalent model-based contrasts.

Between-condition differences (VR vs simulated home) will be derived from the mixed model estimates.

Handling Missing Data

Missing data will be assessed for patterns (missing completely at random, MCAR; missing at random, MAR).

Linear mixed models inherently accommodate missing data under MAR assumptions.

If necessary, multiple imputation will be performed as a sensitivity analysis.

Assumption Checking

Model assumptions will be evaluated:

Normality of residuals (Q-Q plots, Shapiro–Wilk test)

Homogeneity of variance

Linearity

If assumptions are violated, appropriate transformations or non-parametric alternatives will be considered.

Subgroup and Sensitivity Analyses

Where sample size permits, exploratory subgroup analyses may be conducted based on:

Prior clinical experience

Gender

Baseline competency levels

Sensitivity analyses:

Per-protocol analysis

First-period-only analysis (if carryover is present)

Effect Size Reporting

Effect sizes will be reported alongside p-values:

Mean differences with 95% confidence intervals (CI)

Standardized effect sizes (e.g., Cohen's d) where appropriate

Software and Reproducibility

All analyses will be conducted using SPSS v28. Syntax files and anonymized datasets will be retained to ensure reproducibility and auditability.

Project Plan

This project consists of the following four phases: 1) Preparatory phase -Developing two sets of VR CAVE community scenarios; 2) Briefing sessions; 3) Implementing the VR CAVE scenarios; and 4) Data analysis and generating design principles for VR CAVE model for community health nursing.

Phase 1: Preparatory phase

- Obtain HKU/HA HKW IRB.
- Inform and seek advice from Director of BN(FT) Program about the implementation of the project.
- Seek approval on using IAPCC-SV.
- Developing two sets of VR CAVE community scenarios

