The principal investigator will conduct a separate briefing session before the intervention at a mutually convenient time. This session will ensure that they understand all logistics and the knowledge required to guide the students through the cases in the study.

All participants will have a pre briefing time before the start of scenario. The principal investigator will explain the nature, purpose, procedures, risks and benefits of the proposed project to potential participants. Confidentiality and the voluntary nature of participation will be emphasized. Students who agree to participate will sign a consent form. The principal investigator will provide briefings on the project logistics and student expectations to ensure they are fully informed.

Then, students will be asked to take a pre-test and post-test on knowledge, self-confidence, satisfaction, and cultural competence in community health nursing.

Phase 3: Implementing the VR CAVE model

In the second semester, the VR CAVE model will be applied with Year 5 nursing students in the Community & Global Health Nursing (NURS4604) course. Students will form groups and actively participate in conducting home assessments and identifying health hazards for the patient with a play time of 20 minutes. In the proposed study, fifth-year nursing students will interact with a VR CAVE, a virtual reality environment designed to simulate home visits for two unique patients, Stone Wong and May Wong, both situated in a poverty-stricken home setting (Figure 1). With around twenty hidden cues in each case, the VR CAVE provides a realistic and immersive environment that mirrors the patients' homes. These cues symbolize potential health risks and cultural preferences related to health, thus challenging the students to observe, assess, and respond effectively.

Prior to the intervention, an online Qualtrics e-consent will be obtained from the participants. Furthermore, a pre-test will be conducted using the Clinical Competence Questionnaire (CCQ), Student Satisfaction and Self-confidence in Learning (SSS), and Cultural Competence Assessment Instrument (CCA). This will allow us to measure the baseline competencies of the students before the intervention.

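### The first-period fallback has no stated model and no adjustment for the Lab 1 pre-test, which costs precision for CCQ and CCA

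*Combined protocol and SAP*

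**What the plan says.** The design is stated plainly: "This study adopts a two-period, two-sequence crossover randomized controlled design". Under Phase 3, CCQ, SSS and CCA are completed before and after each lab. Of the Lab 1 pre-test the protocol says: "This will allow us to measure the baseline competencies of the students before the intervention". The Lab 2 pre-test comes after the first exposure, and Phase 3 says it is there to pick up changes caused by Lab 1.

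On analysis, the SAP (Primary Analysis) says: "A linear mixed-effects model (LMM) will be used to evaluate intervention effects while accounting for repeated measures and crossover design". Its fixed effects are intervention, period, sequence, time (pre or post) and interactions, with intervention by time as the example. Participant is the random effect. Phase 4 of the project plan gives a similar list: time, group, sequence order and group by time. In both, the pre-test is a response row, and neither list contains a baseline covariate.

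Under Carryover Effect Assessment, if carryover is significant at 0.05, "analysis will be restricted to first-period data only, effectively treating the study as a parallel-group trial". No model follows. The same analysis also appears under Subgroup and Sensitivity Analyses, again without a model. The baseline score is otherwise mentioned only as a possible subgroup factor. The Baseline Analysis section compares the sequences but adjusts for nothing.

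**The concern.** Once the analysis is cut back to Lab 1, the within-student comparison of the two settings is gone, and precision depends on how between-student variation is handled. The Lab 1 pre-test is the only CCQ and CCA score taken before any exposure, so it is the natural covariate for that purpose. The plan collects it from everyone but does not say it will be used this way.

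The likely consequence is a wider confidence interval for the VR CAVE effect than the collected data allow, in the analysis the SAP would fall back on. Because no model is named, the choice between change scores, raw post-tests and adjusted post-tests would also be left until the data are in hand.

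The point is limited to CCQ and CCA. The SSS items in Appendix 2 ask about a simulation the student has just done, so an SSS score taken before Lab 1 is not a baseline in the same sense.

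**Working it through.** **Inputs from the documents.** Two-sided alpha 0.05 (General Principles). 220 students invited (Phase 2); this is the course cohort, not a calculated sample size. There is no stated power, effect size, SD or correlation, so there is no figure of the plan's own to reproduce.

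**Assumptions.** All 220 take part, m = 110 per sequence, complete data, outcome SD = 1 at pre-test and post-test, pre-post correlation rho varied from 0.5 to 0.9.

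**Step 1: what the planned model becomes on Lab 1 data.** Period is constant, and sequence and intervention are the same variable. What remains is group, time and group by time with a participant random intercept. With complete data, the interaction is the difference between groups in mean change, and the group contrast at the post-test is the raw post-test difference. So the model yields either a change-score contrast or an unadjusted post-test contrast.

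**Step 2: variances of the VR CAVE minus simulated home difference.**

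- Change score: 2(1 − rho) × 2/m
- Post-test alone: 2/m
- ANCOVA on the Lab 1 pre-test: (1 − rho²) × 2/m

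Ratios:

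- ANCOVA to change score: (1 − rho²) / [2(1 − rho)] = (1 + rho)/2
- ANCOVA to post-test alone: 1 − rho²

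Both ratios are below 1 for any rho strictly between 0 and 1, apart from the single degree of freedom that the covariate uses.

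**Step 3: worked example at rho 0.5.** Change-score SE = √(2 × 0.5 × 2/110) = 0.135. ANCOVA SE = √(0.75 × 2/110) = 0.117. Multiplying the unrounded SEs by 1.960 + 0.842 = 2.802 gives 80%-power detectable differences of 0.378 and 0.327 SD.

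**Step 4: range of rho.** The power column takes an effect that the change score detects with 80% power and evaluates ANCOVA with noncentrality 2.80 × √(2/(1 + rho)).

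| rho | ANCOVA / change-score variance | Detectable difference, change score (SD) | Detectable difference, ANCOVA (SD) | ANCOVA power when change score has 80% | ANCOVA / post-only variance |
|---|---|---|---|---|---|
| 0.5 | 0.75 | 0.378 | 0.327 | 90% | 0.75 |
| 0.7 | 0.85 | 0.293 | 0.270 | 86% | 0.51 |
| 0.8 | 0.90 | 0.239 | 0.227 | 84% | 0.36 |
| 0.9 | 0.95 | 0.169 | 0.165 | 82% | 0.19 |

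The detectable difference for post-tests alone is 0.378 SD at every rho. At rho 0.5, ANCOVA with 220 × 0.75 = 165 students matches a change-score analysis of 220.

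The variance ratios and the power column do not depend on the number enrolled. The detectable differences do: with 55 per sequence at rho 0.5 they are 0.534 and 0.463 SD.

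**The case against.** Four points can be made against this.

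**The fallback is conditional and its model is inferred.** First-period data become the analysis set only if carryover is significant, and the SAP does not say a change score will be used. This is correct, and it is why the point is framed as a missing specification. It does not remove the cost, because the other natural reading, post-tests alone, is also less precise than ANCOVA.

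**The gain may be small.** Questionnaires repeated around a 20-minute session could correlate highly. At rho 0.9 the gain over the change score is only two points of power. This also stands, although at that rho the loss from comparing post-tests alone is very large.

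**Nothing is invalid.** Under randomisation both the change-score and post-test contrasts are unbiased with correct type I error. This is a matter of efficiency and pre-specification only.

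**A reader might infer that the main crossover analysis loses precision in the same way.** The documents do not support that. The SAP defines its target as follows: "The primary parameter of interest is the intervention effect, estimated as the difference in outcome scores between VR CAVE and simulated home conditions". Intervention by time is only an example of an interaction.

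- If the target is the post-test contrast, adding the Lab 1 score gains 0% under the plan's random-intercept model. It gains about 1% to 7% when within-lab correlation exceeds between-lab correlation (0.6/0.5 to 0.9/0.7).
- Measured against intervention by time, a common Lab 1 mean with a free carryover term would cut variance by 14% at rho 0.5 and 8% at rho 0.7 under compound symmetry.
- With the single participant random intercept kept, that recoding can raise variance. The ratio to the planned contrast is 1.01 at within-lab/between-lab correlations of 0.8/0.5, 1.09 at 0.9/0.6 and 1.20 at 0.9/0.5.

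No recoding of the crossover model is therefore recommended here.

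**Conclusion.** The point holds for the first-period analysis of CCQ and CCA. The plan collects a score before any exposure, names no model for the fallback, and lists no baseline covariate anywhere. Either natural reading gives away precision: 25% of the change-score variance at rho 0.5, falling to 5% at rho 0.9; and 25% of the post-only variance at rho 0.5, rising to 49% at rho 0.7. The sizes rest on assumed correlations and equal variances; the detectable differences also rest on full participation and 1:1 allocation.

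A reader might take the Lab 1 pre-test to be a pre-randomisation measure. The documents place it before the intervention and do not say whether it precedes allocation. Equal expected pre-test scores in the two sequences then also require that knowing the allocation does not shift students' self-ratings. That is plausible but not documented.

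**What to change.** Under Carryover Effect Assessment, state the model: for CCQ and CCA, the first-period analysis is an ANCOVA of the Lab 1 post-test score on randomised sequence, with the Lab 1 pre-test score as covariate. Refer to the same model where the first-period analysis is listed under Subgroup and Sensitivity Analyses. Add that the Lab 2 pre-test is not to be used as a baseline covariate, because it follows Lab 1 exposure.

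The cost is a sentence or two of SAP text, a short piece of SPSS syntax and one degree of freedom. Students without a Lab 1 pre-test need routine handling of a missing covariate, which should be stated. No new data, visits or participants are needed.

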The intervention group will then undergo the VR CAVE experience in Lab 1, while the control group will conduct a simulated home visit in the same lab. After completing the simulated home visit, the students will take an online Qualtrics post-test on the CCQ, CCA, and SSS. This will provide us with data to compare the competencies of the students post-intervention, and to assess the effectiveness of the VR CAVE as a training tool for nursing students.

Following the initial lab session, the two groups will switch settings for the second lab, thus ensuring a comprehensive and balanced assessment of the effects of the VR CAVE intervention.

The intervention group that initially experienced the VR CAVE will now shift to the

conventional simulated home, while the control group will have the opportunity to experience the VR CAVE intervention. This crossover design will provide a holistic view of the students' learning experience in both simulated environments.

Before the second lab session, participants will once again provide e-consent using Qualtrics. This reaffirms the ongoing voluntary nature of their participation. As in the first lab session, students will complete pre-tests using the Clinical Competence Questionnaire (CCQ), Student Satisfaction and Self-confidence in Learning (SSS), and Cultural Competence Assessment Instrument (CCA). This will allow us to monitor any changes in competencies as a result of the initial lab session.

After completing the second lab session, students will perform the same set of post-tests online via Qualtrics based on the CCQ, CCA, and SSS. This will enable us to evaluate any shifts in clinical, cultural, and satisfaction competencies following exposure to both the VR CAVE and the conventional simulated home. This comprehensive testing strategy will ensure that we capture a wide range of data to assess the overall effectiveness and impact of the VR CAVE technology in nursing education. The flow chart is shown in Figure 2.

Figure 1 VR CAVE model for poverty home

[figure not shown]

Figure 2 Flowchart of the study

Phase 4: Data analysis and generating design principles for a VR CAVE model

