The primary and secondary analyses will involve descriptive statistics, including mean and standard deviation, to summarize participants' demographics and scores from the Clinical Competence Questionnaire (CCQ), Cultural Competence Health Practitioner Assessment (CCHPA-129), and Student Satisfaction and Self-Confidence in Learning (SSS). Baseline characteristics of the intervention and control groups will be compared using the χ^2 test or Fisher's exact test for categorical data and the independent t-test for continuous data. The CCQ, CCHPA-129, and SSS scores will be evaluated using a linear mixed-model analysis. Participants will be included as the random effect with time, group, randomization sequence order, and group x time interaction as fixed effects. The analysis will adhere to the intention-to-treat principle,

conducted on subjects as randomized. All statistical analyses will be performed using IBM SPSS version 28.0. All statistical tests will be two-sided with the level of significance set at 0.05.

Design principles specific to the context of the VR CAVE will be generated based on the findings of this project. These design principles will guide and be applied in further designing and developing VR CAVE for community health nursing.

Project schedule

Phase	Estimated Completion Time
1: Preparatory phase	January 2025
2: Briefing session	February 2025
3: Implementing the VR CAVE model	April-August2025
4: Data analysis and generating design principles for a VR CAVE model phase	January 2026

Reference

1. Thompson, C. W., Moscola, S., & Buckland, S. T. (2021). Nursing student perceptions of home visit simulation scenarios. *Nursing education perspectives*, 42(2), 113-114.
3. Alıcı, N. K., & Emiroğlu, O. N. (2020). Students' home visit experiences within the scope of public health nursing course: A qualitative study. *Acıbadem Üniversitesi Sağlık Bilimleri Dergisi*, 12(1), 146-151.
4. Dalton, J. M., Aber, C., & Fawcett, J. (2009). Students' perceptions of home visiting. *Home Healthcare Now*, 27(4), 253-261.
5. Meeley, N. G. (2021). Undergraduate student nurses' experiences of their community placements. *Nurse Education Today*, 106, 105054.

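### Neither mixed model prespecifies period x time, so a difference in gain between Lab 1 and Lab 2 leaks into the VR CAVE gain contrast when the analysed sequences are unequal

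*Combined protocol and SAP*

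**What the plan says.** - **Design.** Study Design Considerations in the SAP: "This study adopts a two-period, two-sequence crossover randomized controlled design". Sequence A has VR CAVE first and sequence B has the simulated home first. The period effect is listed among the key effects to evaluate.
- **SAP model (Primary Analysis).** Participant is the random effect. The fixed effects are intervention, period (1 vs 2), sequence, "Time (pre vs post"), and an open item, "Interaction terms (e.g., intervention" x time being the only example. The Carryover Effect Assessment adds an optional intervention x period term. Period x time is not named.
- **Phase 4 model.** "Participants will be included as the random effect with time, group, randomization sequence order, and group x time interaction as fixed effects". There is no period term of any kind.
- **Target.** "The primary parameter of interest is the intervention effect, estimated as the difference in outcome scores between VR CAVE and simulated home conditions". The SAP does not say whether this means the effect averaged over pre and post, the post-score difference or the difference in gain.
- **Data (Phase 3).** Pre-tests and post-tests are taken in both labs: "As in the first lab session, students will complete pre-tests using the Clinical Competence Questionnaire (CCQ") together with the other two instruments. Each lab therefore has its own gain. Attendance at Lab 2 depends on a further step: "Before the second lab session, participants will once again provide e-consent using Qualtrics".

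**The concern.** In a crossover, adjusting for period should stop a difference between sessions from being read as a treatment effect. Here the data are pre and post scores from two labs, and the named interaction, intervention x time, is a contrast of gains. A period main effect moves both scores of a lab by the same amount and cancels from the gain. The adjustment that acts on gains is period x time, and neither section names it.

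Gains could well differ between labs. Lab 1 is the first simulated visit in the study and the first completion of the questionnaires. The SSS items (Appendix 2) ask about the simulation received, yet the scale is given before Lab 1, when no study simulation has taken place. By the Lab 2 pre-test there has been one. This makes unequal gains plausible, but the documents give no data on it.

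If gains differ and the analysed sequences are unequal, part of the difference is credited to VR CAVE (if sequence A is larger) or to the simulated home (if B is larger).

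**Working it through.** The plan states no sample size calculation, effect size or SD, so there is no figure of its own to reproduce.

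**Inputs from the documents.** Two sequences and two periods; the fixed effects listed in the SAP and in Phase 4; two-sided 5% level (General Principles: "Statistical significance will be set at a two-sided" p < 0.05); 220 students invited (Phase 2), which is an upper limit for N.

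**Assumed inputs.** No true VR effect; a Lab 1 gain of 0.5 SD and a Lab 2 gain of 0.1 SD, so a gap of 0.4 SD (0.2 to 0.6 also tried); residual variance s² of 0.2 to 0.3 of the total; N = 220; the splits and return patterns below.

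**Step 1: what the model leaves in the gain.** Take each student's change (post minus pre) in each lab. The random intercept, intervention, period and sequence main effects all cancel. What remains is a constant (time) plus intervention x time. The estimate is therefore the mean of all VR gains minus the mean of all home gains. VR gains come from A in Lab 1 and B in Lab 2; home gains come from B in Lab 1 and A in Lab 2.

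**Step 2: bias.** With g1 and g2 the gains in Labs 1 and 2, and nA1, nB1, nA2, nB2 the numbers analysed:

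bias = (g1 - g2) x [nA1/(nA1 + nB2) - nB1/(nB1 + nA2)]

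With complete data this is (g1 - g2) x (nA - nB)/N.

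**Step 3: false-positive rate.** With complete data, SE = sqrt(4s²/N). This is sqrt(0.8/220) = 0.060 SD for s² = 0.2 and sqrt(1.2/220) = 0.074 SD for s² = 0.3. The rate follows from normal theory with shift bias/SE. In the last two rows of the table the SE uses the numbers actually analysed.

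| Analysed numbers | Bias with 0.4 SD gap | False-positive rate |
|---|---|---|
| 110/110, complete | 0 | 5% |
| 120/100, complete | 0.4 x 20/220 = 0.036 SD | 8-9% |
| 130/90, complete | 0.4 x 40/220 = 0.073 SD | 17-23% |
| 110/110, then 80 (A) and 104 (B) in Lab 2 | 0.4 x (110/214 - 110/190) = -0.026 SD | 6-7% |
| 110/110, then equal loss | 0 | 5% |

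For gaps of 0.2 to 0.6 SD, the 120/100 row runs from 6% to 15%.

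**Step 4: how likely are such splits?** Under simple 1:1 randomisation of 220, |nA - nB|/N has median 4.5% and 95th percentile 12.7%. A split of 120/100 or worse has probability about 20%; 130/90 or worse, about 0.8%. Averaged over such randomisation, the rate is about 6.6-7.4% for a 0.4 SD gap and 5.4-5.6% for a 0.2 SD gap.

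**Step 5: other contrasts.** The exact expectation of the random-intercept estimator was computed for both written models. The gain bias was the same in both, matched Step 2, and did not change with intraclass correlation (0.3, 0.7 and 0.9 tried at 130/90 in the SAP model). In the SAP model the intervention effect averaged over pre and post had zero bias. The post-score contrast equals that average plus half the gain contrast, so it carries half the bias. In the Phase 4 model the averaged effect is biased too, because nothing adjusts the level. For example, with gains of 10 and 4 points and the Lab 1 gain fully retained, a 120/100 split shifts it by -0.64 points.

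**Step 6: with period x time added.** The bias of the gain contrast is zero at every split and return pattern tried. With complete data the variance becomes s²(1/nA + 1/nB). At 130/90 and s² = 0.2 this is 0.2 x (1/130 + 1/90) = 0.00376, so the SE rises from 0.060 to 0.061 SD, about 1.7%. The eight design cells identify all seven parameters.

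**The case against.** - **The SAP list is open.** A reader might infer that the plan excludes period x time. It does not: the plural and the e.g. leave room for it. What stands is that the term is not prespecified. Phase 4 does not define the levels of time, and a four-level factor (pre and post of each lab) would absorb period x time. The SAP, however, defines time as pre vs post. With group x time, the four-level reading also makes the sequence term redundant (nine columns, rank eight).
- **The primary parameter may not be the gain.** A reader might infer that the period effect contaminates the SAP's VR estimate in general. The documents do not support that. The SAP's period term removes a level shift between labs, and the effect averaged over pre and post is unbiased. The leak concerns the gain contrast and, by half, a post-score contrast. Since intervention x time is the only interaction named, the gain remains a natural reading of the target.
- **The inputs are assumed.** No gains, SDs, split or dropout are documented. Enrolment may fall below 220, which enlarges the SE and makes the same bias matter less. Both sequences face the same renewed consent, and equal loss gives no bias. All of this stands and limits the size of the problem.
- **An allocation ratio may exist.** The visible text gives none, but the flowchart (Figure 2) is not reproduced in the text reviewed. It cannot be said that the plan lacks one. Even equal allocation would not ensure equal attendance at Lab 2.

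**Conclusion.** The point holds as a specification gap of limited size. Following only the terms that are written, the gain contrast is biased whenever the analysed sequences are unequal and the two labs produce different gains. With complete data the bias is exactly the gap in gains times the relative imbalance, and either arm can benefit. Under simple 1:1 randomisation of 220 that is typically about 5% of the gap and rarely above 13%.

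The 8-9% false-positive rate at 120/100 depends on the assumed 0.4 SD gap and the assumed residual share. The 17-23% figure at 130/90 should not be read as an expected error rate, because simple 1:1 randomisation would give such a split less than 1% of the time. Larger leaks would need markedly unequal allocation, for instance if whole student groups were assigned; the text does not say whether students or groups are randomised. Lab 2 attendance that differs by sequence would also cause a leak. The case for the change is that one term removes the bias at almost no cost.

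**What to change.** In both the SAP's Primary Analysis and Phase 4, replace the current wording with one closed list of fixed effects: intervention, period, sequence, time (pre vs post), intervention x time and period x time. This also gives Phase 4 the period main effect it lacks. Keep period x time in the model whatever its p-value.

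State that the VR CAVE effect on gain is the intervention x time contrast from this model. Alternatively, model each lab's change score on intervention, period and sequence, which gives the same estimate with complete data. The SAP should also say which contrast is primary.

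Cost: one extra term in the SPSS syntax, one line of SAP wording and the matching edit in Phase 4. With complete data the SE is multiplied by 1/sqrt(1 - r²), where r = (nA - nB)/N: 1.004 at 120/100 and 1.017 at 130/90.

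### The primary parameter is not tied to the pre-to-post change, so its size, and under one coding its sign, depend on how the intervention effect is read from the model

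*Combined protocol and SAP*

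**What the plan says.** The SAP (Study Design Considerations) sets out the design: "This study adopts a two-period, two-sequence crossover randomized controlled design". Under Phase 3 of the Project Plan, CCQ, SSS and CCA are completed before and after each lab. Of the first pre-test the protocol says: "This will allow us to measure the baseline competencies of the students before the intervention". Of the second, which follows exposure to the other condition, it says: "This will allow us to monitor any changes in competencies as a result of the initial lab session". The last measurement is described thus: "After completing the second lab session, students will perform the same set of post-tests online via Qualtrics based on the CCQ, CCA, and SSS". No washout is described.

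The SAP's Primary Analysis fits a linear mixed model with participant as random effect. Intervention, period, sequence and time (pre or post) are separate fixed effects. The interaction appears only as an example: "Interaction terms (e.g., intervention \times time". The target is then named: "The primary parameter of interest is the intervention effect, estimated as the difference in outcome scores between VR CAVE and simulated home conditions".

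Three other places bear on the contrast, and none settles it:
- The protocol's first primary outcome is framed as a greater increase after VR CAVE than after the simulated home.
- The SAP's section on within-group and between-condition comparisons takes between-condition differences from the mixed model, without saying which estimate.
- Phase 4 lists group-by-time as a definite fixed effect. It names no primary contrast and has no separate period term.

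**The concern.** The effect of a session is what changes between its pre-test and its post-test. The pre-test rows cannot carry the effect of the session whose label they bear. In Lab 1 they precede any exposure. In Lab 2, rows labelled VR, pre-test follow the simulated home, and rows labelled home, pre-test follow VR CAVE. Any learning retained from Lab 1 therefore enters the Lab 2 pre-test under the opposite label.

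An intervention effect averaged over pre- and post-test mixes these rows into the comparison and is pulled toward zero. One read from a coefficient table depends on which time level is the reference. The primary estimate, its confidence interval, its p-value and the planned Cohen's d all rest on this choice.

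**Working it through.** The plan gives no target effect, SD, retention assumption or sample-size calculation, so there is no stated figure to reproduce. The check derives the expected value of each candidate estimate.

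**Assumptions.** The simulated home gives a gain g and VR CAVE gives g+d. A share r of the Lab 1 gain (0 to 1) is still present at the Lab 2 pre-test and post-test. Gains add.

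**Expected scores, relative to baseline**

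| Sequence | Lab 1 pre | Lab 1 post | Lab 2 pre | Lab 2 post |
|---|---|---|---|---|
| A (VR, then home) | 0 | g+d | r(g+d) | r(g+d)+g |
| B (home, then VR) | 0 | g | rg | rg+g+d |

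**VR minus home, averaging the two labs**

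- Pre-test rows: (0+rg)/2 − [0+r(g+d)]/2 = −rd/2.
- Post-test rows: [(g+d)+(rg+g+d)]/2 − [g+r(g+d)+g]/2 = d(1−r/2).
- Time-averaged effect: the mean of these two, d(1−r)/2.
- Intervention-by-time: post minus pre, d(1−r/2) + rd/2 = d.

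The first two are also the intervention coefficient in a reference-coded model with the interaction fitted, with pre-test or post-test respectively as reference.

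| r | Time-averaged | Post-test reference | Pre-test reference | Intervention × time |
|---|---|---|---|---|
| 0 | 0.500d | 1.000d | 0 | d |
| 0.25 | 0.375d | 0.875d | −0.125d | d |
| 0.5 | 0.250d | 0.750d | −0.250d | d |
| 0.75 | 0.125d | 0.625d | −0.375d | d |
| 1 | 0 | 0.500d | −0.500d | d |

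Fitting the SAP's fixed effects to these means gives the same values. Adding period-by-time leaves the interaction at d.

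**Power (illustrative).** Take d=0.3, a residual SD of 0.6, a random intercept only, and all 220 invited students split equally. The standard error of the time-averaged effect is 0.6/√220 = 0.0405; that of the interaction is twice this, 0.0809. At r=0 both tests have the same ratio of effect to standard error (0.15/0.0405 = 0.30/0.0809 = 3.71), and so the same power, 96%. As r goes through 0, 0.25, 0.5, 0.75 and 1, power for the time-averaged effect is 96%, 79%, 46%, 15% and 5%. For the interaction it stays at 96%.

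A second set of assumptions lets scores also vary by lab within a student: 200 students, d=0.3 SD, variance shares 0.5 participant, 0.2 participant-by-period and 0.3 residual. The standard errors are √[(2×0.2+0.3)/200] = 0.0592 for the time-averaged effect and √(4×0.3/200) = 0.0775 for the interaction. Power for the former is about 72% at r=0 (0.15/0.0592 = 2.54), 24% at r=0.5 and 5% at r=1. For the interaction it is 97% throughout.

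**Carryover rule.** Averaged over all rows, the sequences differ by rd/2, so retained learning can itself trigger the SAP's restriction to first-period data. In Lab 1 alone, the time-averaged difference is (g+d)/2 − g/2 = 0.5d, while the difference in change is d.

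**If gains are not additive.** Suppose the Lab 2 gain is reduced by a fraction k of the Lab 1 gain. VR gains then average (g+d) − kg/2 and home gains g − k(g+d)/2. The interaction contrast becomes d(1+k/2): 1.25d at k=0.5, but still 0 when d=0.

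**The case against.** A reader might infer that the plan has chosen the intervention main effect over all rows, so that it recovers at most half of the VR CAVE effect, and none of it if Lab 1 learning is retained. The documents do not support that as a flat statement. The SAP never uses the term main effect and does not say that the difference is taken over all rows. With post-test as reference, the same named effect is worth 50% to 100% of d. Phase 4 includes group-by-time outright, and the protocol's first primary outcome points toward change. Phase 3 says the second pre-test will show any changes from Lab 1; it does not say that gains persist in full. The power figure at r=1 is only the significance level, because the expected estimate there is zero by construction. At r=0 the tests can have equal power.

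All of that stands, and it rules out the unconditional claim. It does not remove the problem. Intervention is a stand-alone term in the SAP, the interaction is only an example there, and no section makes the interaction primary. The time-averaged reading is a natural one. That other readings are open means that the primary result is not fixed in advance. The planned within-condition pre-post tests do not fill the gap, because they do not compare conditions. Nor does the carryover rule, which still gives 0.5d if pre-test rows are averaged in.

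**Conclusion.** The point holds in this form: the SAP names an intervention effect as primary without tying it to the pre-to-post change. Read as a time-averaged effect, it estimates d(1−r)/2. Read as a coefficient, it estimates d(1−r/2) or −rd/2 according to the reference level; under the latter, any retained learning makes an effective VR CAVE appear worse than the simulated home.

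At r=0 the main harm on the time-averaged reading is a halved mean difference and Cohen's d. Any loss of power there depends on the variance structure. As r rises, power falls toward 5%. The expected values rest on additive gains and on retention through Lab 2; the power figures rest also on assumed effects and variances. The documents do not show that the trial will miss a real effect, only that the primary estimate as worded may be diluted and is not uniquely defined.

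**What to change.** Amend the SAP's Primary Analysis and the Phase 4 text together:

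1. For CCQ and CCA, name the intervention-by-time contrast as the primary parameter: VR CAVE minus simulated home in within-lab pre-to-post change, with its 95% confidence interval.
2. Make that interaction a definite term in both places, and add period-by-time so that the average gain can differ between labs. In Phase 4, state the period term and the levels of time.
3. In any first-period-only analysis, use the same change contrast, or the post-test score adjusted for pre-test.
4. State that the time-averaged intervention effect will not be interpreted.
5. State that the contrast equals d only under additive gains and becomes d(1+k/2) if the Lab 2 gain shrinks as above. Period-by-time does not remove this.
6. Give the SSS contrast separately. SSS is a listed primary outcome, but its Appendix 2 items ask about a simulation activity that has not yet taken place at the Lab 1 pre-test.

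The cost is SAP and protocol wording and one contrast statement in the analysis syntax. No new data are needed.
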